1. BACKGROUND AND RATIONALE

In response to the rapid global spread of cases and deaths, the World Health Organization (WHO) characterized the novel Coronavirus Disease 2019 (COVID19) outbreak as a global pandemic on March 11, 2020.¹ Since the initial detection in Wuhan, China in December 2019, the number of COVID-19 cases has reached alarming rates and continues to rapidly increase. As of April 14th, 2020 there have been almost 1,844,863 confirmed cases and 117,021 deaths globally.² Currently there are no antivirals available and therapeutic treatments are limited; numerous clinical research investigations commencing imminently.

1.1 Transmission, clinical presentation and diagnosis of COVID-19

The name of virus responsible for the COVID-19 outbreak, Severe Acute Respiratory Syndrome (SARS) coronavirus 2 (SARS-CoV-2), was chosen based on its genetic similarities with the coronavirus that caused the SARS outbreak in 2003.³ The exact origin of the virus is currently unknown.⁴ Existing literature supports that the novel β-Coronavirus (termed SARS-CoV-2) belongs to the family Coronaviridae, from the order Nidovirales, which are all enveloped, non-segmented positive-sense RNA viruses which may cause illness in humans and animals.^{5,6} The Coronaviridae family of viruses include causative viruses such as Severe Acute Respiratory Syndrome (SARS) and Middle Eastern Respiratory Syndrome (MERS).⁷ Much like influenza and other respiratory viruses, SARS-CoV-2 is primarily transmitted person-to-person through close inhalation of respiratory droplets formed during a cough, sneeze or exhale.⁸ People without the disease can also acquire the infection by touching surfaces contaminated by SARS-CoV-2, defined as fomite transmission.⁹ Clinical manifestations among adults include fever, cough, myalgia, headache and shortness of breath.¹⁰ Severe cases can result in life threatening pneumonia and acute respiratory distress syndrome.¹¹ The incubation period is estimated to be between 1 and 14 days, with 97.5% of cases developing symptoms within 10.5 days (95% Cl: 7.3-15.3) of infection.¹² Due to the small number of cases, it is not yet certain whether pregnancy and childbirth aggravate clinical presentation of COVID-19.

1.2 Implications of COVID-19 infection for pregnant women

Currently, there are limited data on the clinical characteristics of COVID-19 infection in pregnant women, including any adverse impacts on the developing fetus.⁸ Three early case-series reports from China reported a total of 31 pregnancies affected by COVID-19. One of the case series included nine pregnant women in Wuhan, all hospitalized with COVID-19 pneumonia during the third trimester of pregnancy. Clinical manifestations were similar to those reported among non-pregnant adults and included fever, cough, myalgia, malaise and sore throat. No women required mechanical ventilation, there were no maternal deaths and newborn Apgar scores at 1 and 5 minutes were high.¹³ Another case series included 13 COVID-19-infected pregnant women admitted to hospital in other areas of China. The study reported that three of the women were discharged from hospital with an ongoing pregnancy, while the other 10 women were delivered by cesarean, five urgently for fetal indications (three for fetal distress, one for premature rupture of membranes and one stillbirth).¹⁴ The third Chinese case series included 10 live born infants exposed to maternal COVID-19 infection while *in utero* and reported six preterm and two small-for-gestational-age infants. One infant born at 34 weeks' gestation developed complications and died nine days after birth. Other clinical complications in the newborns were also reported, including prolonged hospitalization and respiratory distress.¹⁵

More recently, Breslin et al. reported a case series which included 43 confirmed COVID-19 pregnant women that presented to an affiliated pair of New York City hospitals between March 13 and March 27, 2020.¹⁶ Disease severity among these pregnant women were similar to previous reports in non-pregnant individuals: 86% mild, 9.3% severe and 4.7% critical. None of the neonates were tested positive for COVID-19 through PCR testing of nasopharyngeal swab samples. Although cases were initially identified through routine testing of symptomatic patients, New York City later initiated universal testing of all obstetrical admissions on March 22nd which additionally allowed for the capture of asymptomatic cases. Among the 43 cases reported, an unexpectedly large proportion of patients were initially asymptomatic (n=14) and presented a milder course of disease. Considering 12 of these asymptomatic positive cases were identified through this new universal testing strategy, the authors advocate for universal testing of all pregnant women upon admission for delivery.¹⁶ Although reports of COVID-

19 cases among newborns and young infants have been rare thus far, healthcare providers need to be extra vigilant when assessing newborn babies delivered by infected mothers, as early identification and isolation are imperative to virus control.

1.3 Susceptibility to and severity of COVID-19 in pregnancy

It is well-established that certain infections disproportionately impact pregnant women leading to increased rates of hospitalization and complications, likely due to physiological, physical, and immunological adaptations to pregnancy.¹⁷ Based on the lack of information currently available, we are unable to fully understand the risks and susceptibility of SARS-CoV-2 infection during pregnancy. Di Mascio et al. recently conducted a systematic review reporting pregnancy and perinatal outcomes of CoV spectrum infections during pregnancy.¹⁸ They found a total of 19 case series studies with 79 pregnancies affected by CoV infections: 41 pregnancies in the review (51.9%) were affected by COVID-19, 26 (32.9%) by SARS and 12 (15.2%) by MERS. Among the six studies reporting information on COVID-19 infection during pregnancy, preterm birth (<37 weeks' gestation) was the most commonly reported adverse pregnancy outcome, occurring in 41.1% (95% CI: 25.6-57.6) of cases. These COVID-19 infected pregnant women also had higher rates of miscarriage, pre-eclampsia, and perinatal death, compared to the general population. Whether these complications are a result of COVID-19 infection requires further investigation.

1.4 The effects of previous outbreaks on pregnant women

Coronaviruses (CoV) are a family of single-stranded RNA viruses, named for the appearance of crown-like proteins that project on the viral envelope.⁸ Apart from SARS-CoV-2, two other notable human strains of coronaviruses include SARS-CoV and Middle East respiratory syndrome (MERS) coronavirus (MERS-CoV). The WHO reported 774 and 858 deaths associated with SAS-CoV¹⁹ and MERS-CoV²⁰, respectively. Within a short time interval, the novel SARS-CoV-2 coronavirus has led to more deaths than these two previous strains combined.²¹ Evidence of poor maternal and perinatal outcomes from several other outbreaks of viral respiratory illness over the past 20 years (i.e., 2009 A/H1N1 influenza pandemic,^{22–25} SARS^{26,27} and MERS⁸) indicate a need for enhanced surveillance of pregnant women during this current pandemic to determine whether COVID-19 poses any threat to maternal, fetal or infant heath.

Although SARS and MERS are not identical to SARS-CoV-2, evidence on the effects of these viruses during pregnancy can help to guide obstetrical care and inform control measures.

1.5 Testing for the presence of SARS-CoV-2

According to the WHO, real-time fluorescent quantitative PCR (RT-qPCR or RT-PCR) is currently recognized as the gold standard for clinical detection of SARS-CoV-2.²⁸ Still, RT-PCR is limited by the ability to detect the virus in the sample, and is especially problematic in cases with low viral load in the infected patient's throat,²⁹ resulting in a false negative rate currently reported to be between 30 to 33%.^{30,31} Numerous factors may influence RT-PCR testing results including sample collection and transportation, RNA extraction and degradation in storage, and effective functioning of the kit.³² Despite these limitations of RT-PCR, especially among low viral load specimens, all maternal and neonatal case reports published thus far have only tested for the presence of SARS-CoV-2 using RT-PCR.

Droplet digital PCR (ddPCR), a biotechnological refinement of PCR, has shown improved sensitivity and accuracy for SARS-CoV-2 detection, especially for tests involving low viral load samples.^{28,33} Further, COVID-19 testing using ddPCR has demonstrated lower rates of false negatives and positives, compared to RT-PCR testing.³⁴ Thus, ddPCR can be used in combination with RT-PCR to improve detection and robustness of estimates.

1.6 Mother-to-infant transmission

A crucial question that remains unanswered concerns whether SARS-CoV-2 can be transmitted by the infected pregnant mother to the infant during pregnancy, delivery or post-partum. Mother-to-infant transmission after maternal primary infection can occur during several time periods: intrauterine life via trans-placental viral transfer, delivery via ingestion or aspiration of vaginal secretions and postpartum through breastfeeding.³⁵ Due

to the scarce evidence currently available, the mother-to-child transmission capabilities of SARS-CoV-2 are not yet fully understood.

The small number of studies published thus far have not detected any evidence of vertical transmission from mother to fetus/infant^{13-15,36,37}; however, several newborns have tested positive for SARS-CoV-2 with case studies purporting the potential for vertical transmission.^{38–41} Further assessment is warranted as nearly all of the published findings included women infected during the third trimester of pregnancy and delivered by cesarean section.⁴²

The placenta is a superior example of a pregnancy diary and typically undergoes morphological changes in response to environmental stimuli. A case report of one COVID-19 positive pregnancy found that all collected biological specimens, including a placenta sample, tested negative for SARS-CoV-2.⁴³ Another review of three placentas found no morphological changes related to infection, though all of the women in this case series contracted the virus late in the third trimester and long after the placenta had undergone the bulk of its development.¹³ Furthermore, the role of the SARS-CoV-2 in various placental lesions (e.g., preeclampsia, abnormal placentation, intrauterine growth restriction [IUGR], and disruption of the chorionic membrane) has yet to be explored.

In addition to the consideration of vertical transmission, mothers may pass SARS-CoV-2 onto their infants via breastmilk or combination feeding, similar to women infected with HIV-1. High levels of the HIV-1 virus in the mother increases the RNA viral load in maternal plasma and breastmilk which increases the rate of postnatal transmission by nearly 30%.⁴⁴ The potential for neonatal transmission also includes the impact of aerosol production during the breastfeeding process which warrants additional evaluation. As a result of the unclear and conflicting findings, we cannot rule out the potential for SARS-CoV-2 to permeate through infected breastmilk via consumption or inhalation to infect a nursing infant.

In view of these uncertainties, we propose to undertake a study of COVID-19-infected pregnant women admitted to hospitals for birth across Ontario.

2. AIM & STUDY OBJECTIVE

The overall aim of this research is to generate clinical evidence regarding the impact of COVID-19 infection during pregnancy on maternal, fetal and infant health.

Our objective will be to assess the mother-to-infant transmission potential of SARS-CoV-2 among pregnant women delivering at hospitals across Ontario with confirmed or suspected COVID-19.

3. METHODOLOGY

3.1 Study Design

In order to assess the mother-to-infant and potential vertical transmission of SARS-CoV-2 infection in pregnant women, maternal and neonatal biological samples will be prospectively collected from women with confirmed or suspected COVID-19 at participating hospitals across Ontario. Samples will be tested for the coronavirus serology and viral load.

3.2 Study Setting

The COVID-19 Ontario Pregnancy Event (COPE) Network is a provincial collaboration that was established in response to the pandemic, and currently consists of 12 participating hospitals across Ontario. This network, consisting of physicians and scientists from various institutions across the province, will help unite the resources

and expertise necessary to answer critical research questions related to SARS-CoV-2 infection during pregnancy. The current list of participating sites can be found in **Section 6.1**.

3.3 Study Population

The study population will consist of pregnant women with confirmed COVID-19 at any point during pregnancy or suspected COVID-19 at time of delivery (as identified at local hospital), who will be delivering at a participating hospital within Ontario (current list of participating sites can be found in **Section 6.1**).

3.4 Recruitment

In this global emergency of COVID-19, information regarding the effects of infection during pregnancy are urgently required to help inform obstetrical recommendations, guidelines and practice. Given the low number of cases reported thus far, any pregnant woman admitted to a participating hospital with either suspected or confirmed COVID-19 infection, at any point during pregnancy, will be included in the study.

To facilitate rapid generation of evidence, ensure complete capture of cases, and prevent unnecessary burden on healthcare professionals, we will use an alteration to the consent procedures. This study poses minimal risk to the participants, and given the current circumstances of a global pandemic, and the additional precautions to manage this population, an alternation to the consent requirements are justified to ensure that this research can be carried out.⁴⁵ Using a verbal consent script, the healthcare provider will explain the research study and collection of samples to the participant. Verbal consent will be obtained at a pre-natal visit (in-person, virtual, or telephone), at the time of admission or prior to delivery. If the healthcare provider is unable to obtain verbal consent prior to delivery, sample collection will proceed and consent will be obtained prior to breastmilk and/or neonatal nasopharyngeal swab collection. At this time, consent for use of any previously collected samples will also be sought.

3.5 Study Outcomes

Outcomes for the study objective will be ascertained through the collection and testing of biological samples from the mother and/or infant. Specifically we will:

- 1) Assess maternal nasopharyngeal or oropharyngeal swab, vaginal mucosa, ano-rectal swab, amniotic fluid, placenta (including subamniotic swab), breastmilk, cord blood and neonatal nasopharyngeal swab for RNA particles of coronavirus, by ddPCR.
- 2) Assess maternal serum for anti-coronavirus antibodies, by immunoassay.
- 3) Examine the impact of coronavirus on the neonate with respect to serology and viral load, in addition to placenta pathology findings and ddPCR.
- 4) Assess vertical transmission and the effect of coronavirus through placental pathology examination using placental pathology synoptic report (**Appendix 2**).

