3.6 Data Collection

3.6.1 Timing of Sample Collection

Upon admission to labour and delivery, and prior to delivery wherever possible, the following maternal sample types will be collected: nasopharyngeal or oropharyngeal swab, peripheral blood, ano-rectal swab and vaginal mucosa collected through a vaginal swab. At delivery, wherenever possible, we will collect an amniotic fluid sample through direct syringe aspiration. Should the maternal biological samples not be able to be collected prior to or during delivery, samples may be collected post-delivery, prior to discharge.

Immediately following delivery, we will collect cord blood and placenta samples (including submaniotic swab). Prior to discharge from the hospital, we will collect a neonatal nasopharyngeal swab sample (approximately 12-24 hours post-birth) and a breastmilk sample (nearest to first lactation as possible). The timing of sample

collection is summarized in **Table 2** presented below. Pathologists at each participating site will be requested to send the local placenta pathology report and slides (or scanned slides if slides are not feasible), collected as per standard of care.

Table 2. Timing of biological sample collection

	Timing of sample collection				
Biological sample	Prior to delivery	At delivery	Post deliver	ТY	
Maternal peripheral blood	Х				
Maternal nasopharyngeal or oropharyngeal swab	Х				
Maternal vaginal mucosa	X (swab prior to ۱ membranes, if				
Maternal ano-rectal swab	Х				
Amniotic fluid		Х			
Cord blood		X (from blood gases)			
Placenta (includes subamniotic swab)			X (ex vivo)		
Neonatal nasopharyngeal swab			X (12-24 hours po	st-birth)	
Breastmilk sample			Х		

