We will summarize the nucleic acid test results of all clinical samples collected (vaginal mucosa, amniotic fluid, cord blood, placenta, maternal nasopharyngeal/oropharyngeal and neonatal nasopharyngeal swab, breastmilk) to ascertain the possibility of intrauterine vertical transmission and post-partum feeding transmission. A positive test result reflects the presence of coronavirus in these clinical samples and will be indicative of possible mother-to-infant transmission. Laboratory test results however will be considered within the context of clinical observations and epidemiological data when making the final diagnosis decisions. In addition, binary logistic regression will be conducted to further investigate the association between coronavirus in placenta and the presence of fetal/neonatal complications.

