4.2.2 Antibody Testing

IgG, IgM and IgA antibodies to coronavirus will be evaluated in maternal and cord blood samples to assess whether patients (mothers and infants) have been recently exposed to the virus. IgG, IgM and IgA levels will be measured using a commercially available colorimetric enzyme-linked immunosorbent assay (ELISA), with all reagents prepared as per the manufacturer's protocol.

•		

6. Addition of maternal and cord blood sample data from the INVIVO-P Biobank to the COPE Network dataset

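### Maternal blood is assigned antibody testing only, so an RNA-positive placenta or cord blood specimen, read on its own, cannot be told apart from virus in admixed maternal blood

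*Combined protocol and SAP*

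**What the plan says.** Section 3.6.1 lists the maternal samples taken on admission: "nasopharyngeal or oropharyngeal swab, peripheral blood, ano-rectal swab and vaginal mucosa collected through a vaginal swab". They are to be taken before delivery where possible, otherwise after delivery and before discharge.

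Two places assign an assay to maternal blood, and both are serological. Section 3.5, item 2, reads "Assess maternal serum for anti-coronavirus antibodies, by immunoassay". Section 4.2.2 says "IgG, IgM and IgA antibodies to coronavirus will be evaluated in maternal and cord blood samples".

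Two places list the specimens for viral RNA, and neither includes maternal blood. Section 3.5, item 1, reads "Assess maternal nasopharyngeal or oropharyngeal swab, vaginal mucosa, ano-rectal swab, amniotic fluid, placenta (including subamniotic swab), breastmilk, cord blood and neonatal nasopharyngeal swab", all by ddPCR. The summary in Section 4.2.1 covers "vaginal mucosa, amniotic fluid, cord blood, placenta, maternal nasopharyngeal/oropharyngeal and neonatal nasopharyngeal swab, breastmilk".

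Section 4.2.1 uses these results to look for intrauterine and feeding transmission. It takes a positive specimen as a pointer to possible passage from mother to infant, and adds that laboratory results will be weighed against the clinical and epidemiological context. It also plans a binary logistic regression of fetal or neonatal complications on the presence of virus in the placenta.

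**The concern.** Mother-to-infant transmission is the study's only stated objective (Section 2), and Section 1.6 names transfer across the placenta as one route. Placenta and cord blood are the specimens most naturally read as evidence for that route, and both can carry maternal blood. According to Table 2, cord blood comes from the blood-gas sample, and no check for maternal admixture is described.

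If a mother has viral RNA in her blood at delivery, her placenta or cord specimen may test positive although no virus reached the fetus. The result that would flag this is RNA in maternal blood, and no such test is assigned. If true transmission is rare, a few positives of maternal origin could change the study's main conclusion. Section 7.2 expects the findings to inform practice on delivery and feeding. In the regression, the same mechanism could place women in the exposed group because of their own viraemia.

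**Working it through.** The documents give no figure for this point, so there is none to reproduce. The check sets specimens against assays and then illustrates the possible size.

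**Specimens against assays**

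| Specimen | Collected (3.6.1) | RNA list, 3.5 item 1 | RNA list, 4.2.1 | Antibody |
|---|---|---|---|---|
| Maternal blood | yes | no | no | yes (3.5 item 2, 4.2.2) |
| Cord blood | yes | yes | yes | yes (4.2.2) |
| Placenta | yes | yes, with subamniotic swab | yes, swab not separated | – |
| Amniotic fluid | yes | yes | yes | – |
| Neonatal swab | yes, about 12-24 h | yes | yes | – |
| Maternal naso-/oropharyngeal swab | yes | yes | yes | – |
| Vaginal mucosa | yes | yes | yes | – |
| Ano-rectal swab | yes | yes | no | – |
| Breastmilk | yes | yes | yes | – |

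Maternal blood is the only collected specimen absent from both RNA lists. The list in 4.2.1 also leaves out the ano-rectal swab, so that list alone is weak evidence. The omission rests mainly on 3.5.

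**Illustration of size**

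From the documents: N = 150 to 200 (Section 4.1, which allows for more). The remaining inputs are assumptions:

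- v, mothers with RNA in blood at delivery: 2% to 15%
- f, share of those whose blood alone makes the placenta positive: 10% to 50%
- t, true in-utero infection, each case giving a positive placenta: 1% to 3%
- the two sources of positives do not overlap

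Maternal share of positives = v·f / (v·f + t).

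- Lowest: v·f = 0.02 × 0.10 = 0.002; 0.002 / (0.002 + 0.03) = 0.0625, about 6%.
- Highest: v·f = 0.15 × 0.50 = 0.075; 0.075 / (0.075 + 0.01) = 0.88, about 88%.

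In counts, maternal-origin positives run from 150 × 0.002 = 0.3 to 200 × 0.075 = 15. True positives run from 150 × 0.01 = 1.5 to 200 × 0.03 = 6.

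**Reflex assays needed**

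As an upper bound, let every viraemic mother give a positive placenta (f = 100%).

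- Low end: 150 × 0.02 + 150 × 0.01 = 3 + 1.5 = 4.5.
- High end: 200 × 0.15 + 200 × 0.03 = 30 + 6 = 36.

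That is about 5 to 36 reactions.

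**The case against.** The strongest reply is that the plan does not rest on one specimen. For each pair it also seeks amniotic fluid, a subamniotic swab, a neonatal swab, cord IgM and IgA, and placental pathology. Section 4.2.1 speaks only of possible transmission and promises to read results in context. A reader might infer that the study cannot separate maternal from fetal virus at all. The documents do not support that: the ambiguity belongs to a placenta or cord blood specimen read alone. What stands is that 4.2.1 states no rule for combining the specimens. Each has limits: a swab at 12-24 hours can reflect exposure during or after birth, cord antibody shares the admixture problem, and the subamniotic swab is not separated from placenta in 4.2.1.

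Three other strong readings also fail.

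- *Most RNA-positive placentas would be maternal in origin.* Setting f = 100% gives a share of 40% (0.02 / 0.05) to 94% (0.15 / 0.16), but that requires every viraemic mother to produce a positive placenta. Section 3.3 admits women infected at any point in pregnancy, and suspected cases, which favours lower viraemia at delivery.
- *The protocol itself treats maternal plasma load as the driver of placental transfer.* The sentence beginning "High levels of the HIV-1 virus in the mother increases the RNA viral load in maternal plasma and breastmilk" (Section 1.6) concerns HIV and postnatal transmission through breastmilk.
- *The regression equates placental RNA with fetal infection.* It does not. It relates placental RNA to complications, and the problem there is possible misclassification of exposure.

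Finally, Section 3.1 says in general terms that samples will be tested for serology and viral load, and Figure 1, the contents of Table 3 and the Lab Manual are not available here. A maternal blood RNA test named only there cannot be excluded. If one exists, the remedy is to state it in 3.5 and 4.2.1.

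**Conclusion.** The point holds in a limited form. In the available text, maternal blood is drawn and assigned antibody testing only. A positive placenta or cord blood specimen read alone therefore cannot be distinguished from maternal virus in admixed blood, and the placental exposure in the regression may be misclassified for the same reason.

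The size is unknown. The range of about 6% to 88% depends entirely on assumed rates and on treating the two sources of positives as separate. It shows that the problem could be trivial or dominant, and it is not an estimate. The recommendation does not depend on where in that range the truth lies: the change is cheap, needs no new patient procedure and bears on the study's sole objective. It is an improvement worth making and does not invalidate the design.

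**What to change.** 1. Add maternal peripheral blood to the ddPCR lists in Sections 3.5 and 4.2.1. At minimum, run reflex ddPCR on available, RNA-suitable maternal blood for each pair with an RNA-positive placenta or cord sample. Record whether that blood was drawn before or after delivery.
2. Pre-specify labels for those pairs: *maternal viraemia present, maternal origin not excluded* if maternal blood is positive; *maternal viraemia not assessed* if it is untested or unsuitable.
3. State that a positive neonatal swab at 12-24 hours does not by itself classify a pair as intrauterine transmission.
4. Report the subamniotic swab separately from placental tissue.
5. If numbers allow, repeat the placental-RNA regression as a sensitivity analysis excluding pairs with maternal viraemia.

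Cost: about 5 to 36 extra reactions for reflex testing under the upper-bound assumptions, or 150 to 200 if every mother is tested, with an assay already in the plan. The main limit is supply. The current version is 11.0, dated November 2024, and Section 6.1 (Rationale) describes serology on study samples as already done, so some blood may be gone or unfit for RNA work. Items 2 to 4 still apply in that case and need no new assay.
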